The pathology department will handle the cyst fluid; at least 0.5 ml is centrifuged to generate deposit and supernatant fluid. The deposit will be used to process a smear and/or cellblock, for pathological analysis. The supernatant fluid will be sent out to the laboratory for biochemical analysis (CEA, CA 19.9, amylase). If at least 0.5 ml of the cyst fluid is left after the above mentioned procedures, this should be stored and frozen at

minus 80 degrees Celsius, for future molecular analysis. This step will be omitted in centers without such freezing facilities.

The pathologist will be provided with a protocol regarding the aspects that need to be addressed in the pathology report. On request, the pathologist of the investigators team (KB) can be consulted for advice or a second opinion. If surgery is performed, a glass slide of the pathological specimen (or a histological sample, preserved in formalin) must be sent to the pathology department of the Erasmus Medical Center in Rotterdam, for revision.

Laboratory investigations

To determine the serum CA 19.9 level, a blood sample of at least 6 ml must be collected. For each hospital, the local laboratory technique and cut-off value for CA 19.9 will be applied and recorded. In addition, for future genetic testing, two additional 6 ml blood samples will be drawn (one EDTA, one Serum tube) and stored at –20 and -80 degrees Celsius, respectively. This only applies for participating centers with such facilities.

Collection and storage of samples

All human samples that are collected during the study will be stored locally. If local facilities are not sufficient, samples may be sent to the Erasmus University Medical Center Rotterdam, for storage.

Patient questionnaires

Patients with a newly diagnosed cyst will be asked to fill out a questionnaire at home (Table V). This questionnaire will be sent to them by email (if they gave permission to do so) at study entry, after every follow up visit for the first three years, once after 5 and 10 years, and after cyst related events. The questionnaire can be filled out on-line, which will take approximately 5 to 15 minutes. Patients who fail to respond to the questionnaire will be reminded by email after two weeks. Patients who do not want to provide their email address will be able to join the study, without participating in the questionnaire evaluation.

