8.1 Descriptive statistics

Baseline patient and cyst characteristics will be described (Table IV). Also, descriptive of the primary and secondary endpoints will be given. This will be performed for the total cohort and the following sub-populations: 1. unspecified cysts and suspected side-branch IPMN's, 2. newly and previously diagnosed cysts, and 3. cysts followed by EUS and MRCP. For each (sub)population, the follow-up duration, visit frequencies, and numbers lost-to-follow-up will be reported.

Depending on distributional properties of the observed variable, percentages, means \pm standard deviations (SD), or medians with interquartile ranges (IQR) will be reported. Statistical significance will be assessed with use of the Student's t-test for normally distributed continuous data; either the chi-square test for categorical data (with Yates' correction when appropriate) or Fisher exact test for categorical data; and the median test for non-normally distributed continuous data. All reported p-values will be two-sided and a value < 0.05 will be considered to be significant. Data will be analysed with SPSS 22 (or newer), Statistical Package for the Social Sciences (SPSS Inc, Chicago, Illinois).

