8.2 Univariate analysis

For the primary endpoints, univariate comparisons will be conducted, to identify individual patient and cyst risk factors for malignancy (Table IV). As primary potential risk factors are considered; 1. Cyst size, 2. Cyst growth, 3. Mural nodules/solid components, 4. increased serum CA 19.9, 5. Pancreatic duct dilatation, and 6. Patient age. Survival analysis techniques and Cox regression with time-dependent recurrent covariates measures will be applied to assess significance.

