8.3 Multivariate analysis

Multivariate survival analysis will only be performed if the number of events will be > 30 . This is expected to be the case for the primary endpoint. The potential risk factors, given above, will have first interest. A statistical program (MPlus) will be used to perform multilevel analysis of longitudinal data (repeated measures), to analyze changes over time for the different patient reported outcomes, such as cancer worries, anxiety, and depression[20].

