Insulin use	Pancreatic duct communication (Y/N)	
Smoking	Main pancreatic duct dilatation (Y/N)	
Alcohol abuse	Common bile duct dilatation (Y/N)	
	Calibre change main PD (Y/N)	
Serum CA 19.9 level		

Table V: Patient Questionnaire

I. History and background (to evaluate risk factors)
 
Height and weight
 
Smoking and drinking habits
 
History of pancreatitis, pancreatic cysts/cancer/surgery, Diabetes, and insulin use
 
Family history of pancreatitis, and breast/colon or pancreatic cancer

II. Worries and burden of investigational procedures
 
Burden of imaging (MRCP/EUS/CT)

III. Questions regarding the general burden of surveillance and cancer worries
 
Regular checking of a pancreatic cyst...
 
 - Is a good way to detect cancer in time. - Lessens my fear to get cancer. - Gives me a sense of security. - Can lead to unnecessary uncertainty. - Is not important to me, since it will be too late to change the outcome of the disease anyway 
To what extent...
 
 - Do you find the check-ups burdensome? - Do the advantages of the check-up outweigh the disadvantages for you? - Are you nervous when you have to come for your check-up visit? - Do you dread the next check-up visit? 
How often would you like to have your pancreatic cyst checked?
 
For how long would you like to be checked?
 
Did the cyst surveillance change the extent to which you worry about cancer?

IV. Hospital Anxiety and Depression Scale
 
I feel tense or wound up.
 
I still enjoy the things I used to enjoy.
 
I get a sort of frightened feeling, as if something bad is about to happen.
 
I can laugh and see the funny side of things.
 
Worrying thoughts go through my mine.
 
I feel cheerful.

I can sit at ease and feel relaxed.

I feel as if I am slowed-down.

I get a sort of frightened feeling, like butterflies in my stomach.

I have lost interest in my appearance.

I feel restless and have to be on the move.

I look forward with enjoyment to things.

I get sudden feelings of panic.

I can enjoy reading a good book or watching a radio or TV programme.

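### Section 8.2 prioritises CA 19.9 as increased or not, while Table IV, to which it refers, lists the level; the prioritised form is the less informative one if the effect on malignancy is graded

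*Protocol*

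**What the plan says.** Section 8.2 announces univariate comparisons for the primary endpoints "to identify individual patient and cyst risk factors for malignancy (Table IV"). It then singles out six primary potential risk factors. Cyst size, cyst growth and patient age are named as quantities; the tumour marker is named as a state, "4. increased serum CA 19.9". The analysis is described as survival methods and "Cox regression with time-dependent recurrent covariates measures will be applied to assess significance".

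The only account of what would count as increased is under Laboratory investigations in 6.3: "For each hospital, the local laboratory technique and cut-off value for CA 19.9 will be applied and recorded".

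Table IV in the Addendum lists the "Serum CA 19.9 level". It marks several morphology items as Y/N but puts no such mark on CA 19.9.

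Section 8.3 gives the six factors priority and adds that "Multivariate survival analysis will only be performed if the number of events will be > 30". Section 8.1 sets the test level: "All reported p-values will be two-sided and a value < 0.05 will be considered to be significant".

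**The concern.** Read together, 8.2 and 6.3 make the prioritised covariate a yes/no indicator whose threshold differs between hospitals. Table IV points to the level. An analyst following the protocol could defend either form, and the choice could be made after the data are seen.

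The form in the priority list carries less information. A yes/no covariate ignores all variation on either side of the limit. In a time-dependent model, it does not register a rise that stays within the normal range, or a further rise above the limit. Nor can it show whether another threshold, or the change over time, would discriminate better. Risk factors for malignancy feed the secondary objective of better surveillance strategies, and malignancies may be few. A real graded association could therefore be missed.

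**Working it through.** **The protocol's own figures.** It states no power, hazard ratio, distribution of CA 19.9 or share of patients elevated, so there is no power figure to reproduce. On events, 8.3 says only that more than 30 are expected for the primary endpoint, without saying which of the two endpoints is meant.

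- The rationale's rate of 0.0002 per year, with 5000 patients and an assumed mean follow-up of 5.5 years (27,500 patient-years), gives 0.0002 × 27,500 = 5.5 malignancies.
- A cumulative 1 to 3% of 5000 gives 50 to 150.

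I therefore show several event counts: 31 (the smallest that meets the 8.3 condition), 49 (for example 4500 patients × 5.5 years × 0.002 per year = 49.5) and 100.

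**Assumptions.** The log level is normal; 5, 10, 20 or 30% of patients are elevated; the hazard ratio (HR) is per SD of the log level; the test is two-sided at 0.05; the endpoint is malignancy and is rare.

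**Continuous term.** Power = Φ(√D · ln HR − 1.96), where D is the number of events.
- D = 31, HR 1.5: √31 × 0.405 = 2.26; Φ(0.30) = 62%.
- D = 49, HR 1.5: 7 × 0.405 = 2.84; Φ(0.88) = 81%.

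**Yes/no term.** With rare events, the log level among cases is shifted up by ln HR. The share of cases above cut c is therefore p1 = 1 − Φ(c − ln HR). For HR 1.5, p1 is 10.8, 19.0, 33.1 and 45.3% when 5, 10, 20 and 30% of the cohort are elevated. The number of elevated cases is binomial(D, p1). The score test rejects when |k − Dp| ≥ 1.96 √(Dp(1 − p)). Example: D = 31, p = 10% needs k ≥ 3.1 + 1.96 × 1.67 = 6.4, so 7 or more; P(k ≥ 7 | 19.0%) = 38%.

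| Events, HR per SD | Continuous | Yes/no at 5 / 10 / 20 / 30% elevated | Loss (points) |
|---|---|---|---|
| 31, 1.3 | 31% | 26 / 19 / 23 / 21% | 5–12 |
| 31, 1.5 | 62% | 43 / 38 / 46 / 43% | 16–24 |
| 49, 1.5 | 81% | 43 / 46 / 58 / 68% | 13–38 |
| 100, 2.0 | >99% | 98 / >99 / >99 / >99% | 0–2 |

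The yes/no figures are uneven because k is a small integer: at 31 events and 5% elevated, the true size of the score test is 6.7%, which flatters the 26% and 43%. Simulation gave 44% rather than 43% for the lowest entry at 49 events.

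**Cross-check.** The local efficiency of a cut is φ(c)²/[p(1 − p)] = 0.22, 0.34, 0.49 and 0.58 at 5, 10, 20 and 30% elevated. Multiplying ln HR by its square root gives 26, 35 and 40% at 31 events, HR 1.5 and 10, 20 and 30% elevated. That is a larger loss than in the table, so the table is not the pessimistic view.

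**Two checks against the point.**
- *Assay noise.* If the raw level carries between-assay noise of 0.3, 0.5 or 1.0 SD, ln HR shrinks by 1/√(1 + s²). Continuous power at 31 events and HR 1.5 falls from 62% to 58, 52 and 36%. At 1.0 SD the advantage over the cut is gone.
- *Step effect.* If the hazard triples exactly at the cut-off with 10% elevated, the share of cases elevated is 0.3/(0.3 + 0.9) = 25%. At 31 events, P(k ≥ 7 | 25%) = 69% for the yes/no term, against a simulated 38% for the continuous term.

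**The case against.** A reader might infer that CA 19.9 will be analysed only as a dichotomy. The protocol does not say so. Section 8.2 refers to Table IV, and Table IV lists the level, so the level remains a candidate in the same univariate analysis. Section 8.2 states no coding for any of the six factors, and the local cut-off in 6.3 is needed in any case for the resection criteria in Table I. Coding detail may also sit in an analysis plan that is not shown. This removes any claim that the level is excluded. It does not remove the mismatch: the protocol itself chose a word for the prioritised factor, and that word disagrees with its own table.

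A reader might also infer a fixed power loss at the study's expected number of events. The documents do not support that either. The figure of 30 is a condition for the multivariate model, the rate in the rationale would give far fewer malignancies, and the HR and share elevated are assumptions. Over plausible inputs the loss is sometimes negligible.

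Local cut-offs also have a rationale, because techniques differ between hospitals and equal readings need not mean the same thing. That stands against using the raw level. It does not stand against the level divided by the local limit, which removes differences that move level and limit by the same factor, though not all assay noise.

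Finally, 8.2 covers both primary endpoints. Elevated CA 19.9 is itself a relative criterion in Table I, so for the resection-indication endpoint the covariate is partly built into the outcome. The power argument does not carry over cleanly there.

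**Conclusion.** The point holds as a mismatch with a conditional cost. Sections 8.2 and 6.3 together read as a hospital-specific yes/no factor, Table IV lists the level, and 8.3 gives priority to the less informative form.

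For malignancy with a graded effect, the cut loses about 16 to 24 points at 31 events and HR 1.5 per SD, and about 13 to 38 points at 49 events. It loses 5 to 12 points at 31 events and HR 1.3, and almost nothing at 100 events and HR 2.0. These figures rest on a normal log level, 5 to 30% elevated, a single covariate value per patient and no assay noise, none of which the protocol gives. Assay noise reduces the gain, and a pure step effect at the cut-off reverses it. This is an inexpensive improvement, not a flaw that threatens the study.

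**What to change.** In 8.2, replace the fourth factor by: *serum CA 19.9 as log2 (level / local upper limit), continuous and time-dependent*. State that this term enters the 8.3 model for malignancy. Report elevated versus not elevated by the local limit as a secondary coding, so that the result can be read against Table I. The resection criteria in Table I stay as they are.

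The change is one or two sentences and needs no new data: the level is listed in Table IV, and 6.3 already has the local technique and cut-off recorded. The cost is one extra coding to report, and less power in the main coding if the true effect is a step at the cut-off. The secondary coding covers that case.

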8.3 Multivariate analysis

Multivariate survival analysis will only be performed if the number of events will be > 30 . This is expected to be the case for the primary endpoint. The potential risk factors, given above, will have first interest. A statistical program (MPlus) will be used to perform multilevel analysis of longitudinal data (repeated measures), to analyze changes over time for the different patient reported outcomes, such as cancer worries, anxiety, and depression[20].

8.4 Interim analysis

Is described above as the first analysis report

9. ETHICAL CONSIDERATIONS

9.1 Regulation statement

This study will be conducted according to the principles of the Declaration of Helsinki (sixth version, 2008) and in accordance with the Medical Research Involving Human Subjects Act (WMO).

9.2 Recruitment and consent

The treating physician will inform eligible patients about the study and will explain the aims, methods, anticipated benefits, and potential hazards. Also, this information will be provided in print. Subsequently, patients will have at least 48 hours to decide if they want to participate in the study, by giving their written informed consent. If patients have any further questions, they can consult an independent physician (MS in the Netherlands).

9.3 Objection by minors or incapacitated subjects

Not applicable

9.4 Benefits and risks assessment, group relatedness

Participation to the study does not cause any risk for patients, because the surveillance schedule does not differ from the present follow-up recommendations. The only possible burden may be the fact that two extra blood samples will be taken and that participants with a newly diagnosed cyst are invited to complete an online questionnaire. Completing the questionnaire will take no more than 5 to 15 minutes. Subjects may benefit from the active approach towards compliance to the cyst surveillance program. This will minimize the risk of patients getting lost to cyst follow-up.

9.5 Compensation for injury

The sponsor/investigator has a liability insurance, in accordance with article 7, subsection 6 of the WMO.

Because the study is without risks, dispensation from the obligation to provide insurance for the participating subjects was granted by the METC of the Erasmus Medical Center.

9.6 Incentives

Not applicable

10. ADMINISTRATIVE ASPECTS AND PUBLICATION

10.1 Handling and storage of data and documents

10.1.1 Responsibilities of the investigator

The principal investigator is responsible for the conduction and completion of the study. The principal investigator ensures to have appropriate facilities and adequate staff that are fully instructed regarding the study protocol and study procedures.

10.1.2 Electronic Case Record Form (eCRF)

During the course of the study, all collected data will be recorded in an eCRF. The eCRF will be completed timely and fully, according to the protocol. The investigators are responsible for the quality of the data recording. In the event of a protocol deviation, the 'nature of' and 'reasons for' the deviation will be recorded in the hospital record. If the deviation is linked to the content of the CRF, the CRF will also be adjusted. The principal investigator of each participating center is responsible for visit approval.

10.1.3 Privacy rules

The handling of personal data will comply with the Dutch Personal Data Protection Act (in Dutch: De Wet Bescherming Persoonsgegevens, Wbp). All outcome data will be provided by the treating physician through a secured, online eCRF. Patients will be identified in the eCRF by study-number. The investigators will keep an identification log, consisting of the information to link source records to the eCRF.

Patients will complete their questionnaires online. For this purpose, patients will be asked to provide their email address in the informed consent form. This email address will be stored in a separate database, and will only be used to send an email to the patient after every visit. The link between email address and patient is not visible for unauthorized persons and will only be used to serve as an identification key for the electronic system, to be able to couple the study number in the main eCRF to the corresponding respondent in the questionnaire database.

The data are stored and processed using a database program for personal computers. Anonymous data are stored separately from identifiable data (i.e. a patients email address), so that it is impossible to couple research data to specific individuals. All data that leaves the investigational site will be blinded and

anonymized. Only authorized study team members are able to view certain non-anonymous data. For analysis, the anonymous study data from both the clinical and the questionnaire database will be exported and subsequently coupled. From this overall mother-database, data will be transferred to a statistical program. Only anonymized data will be transferred to the statistician for further analysis.

The subjects will be informed that the data will be stored on paper and electronically, that local regulations for the handling of computerized data will be followed as described in the written patient information, and that identification of individual patient data will only be possible for the coordinating and principal investigator. Furthermore, the subjects will be informed about the possibility of inspections of relevant parts of the hospital records by health authorities. These officials will be identified and have signed a confidentiality agreement.

10.1.4 Archiving of data

Patient identification log, hospital records (source documents), informed consent forms, and clinical databases must be kept for at least 15 years after completing the study. If the principal investigator and/or coordinating investigator moves or retires, he/she must nominate someone in writing, to be responsible for record keeping. Archived data may be held on electronic record, provided that a back up exists and a hard copy can be obtained, if required.

10.2 Amendments

Amendments are changes made to the research after a favourable opinion by the accredited METC has been given. All amendments will be notified to the METC that gave a favourable opinion.

10.3 Annual progress report

The investigator will submit a summary of the progress of the trial to the accredited METC once a year. Information will be provided on the date of inclusion of the first subject, numbers of subjects included and numbers of subjects that have completed the trial, serious adverse events/ serious adverse reactions, other problems, and amendments.

10.4 End of study report

The investigator will notify the accredited METC of the end of the study within a period of 8 weeks. The end of the study is set in August 2024, when the 10-year follow-up period has ended. In case the study is ended prematurely, the investigator will notify the accredited METC, including the reasons for the premature termination. Within one year after the end of the study, the investigator/sponsor will submit a final study report with the results of the study, including any publications/abstracts of the study, to the accredited METC.

10.5 Public disclosure and publication policy

The rules for public disclosure and the publication policy are formulated in the “Consortium Agreement of the PACYFIC study group; rules for publication, authorship and ownership of data”.

10.6 Authorship rules

See paragraph 10.5

12. ADDENDUM

Figure 2; Flowchart of pancreatic cyst surveillance, based on the recommendations of the consensus statement by the European study group on cystic tumours of the pancreas[1].

[figure not shown]

Table I: Resection criteria, as recommended in the consensus statement by the European study group on cystic tumours of the pancreas [1].

Resection criteria for cystic neoplasms of the pancreas		

 - 1. Cysts \geq 4 cm in size - 2. Cysts diagnosed as 
 - Mucinous Cystic Neoplasm (MCN) - Main-duct Intraductal Papillary Mucinous Neoplasm (MD-IPMN)), - Solid Pseudopapillary Neoplasm (SPN) - 3. Presence of risk factors* for malignancy (\geq1 absolute or \geq 2 relative) 		
* Risk factors	Absolute criteria	Relative criteria
Cyst related	
 - Mural nodules - Dilatation Main Pancreatic Duct (MPD) $>$ 6 mm - Eggshell calcifications 	
 - Significant growth
Patient related	
 - Jaundice - Acute pancreatitis - Diabetes 	
 - Elevated serum CA 19.9 - Epigastric pain - Weight loss

Table II: Types of pancreatic cyst resection

Surgical procedure
Pylorus preserving pancreaticoduodenectomy or classic Whipple procedure
Duodenum preserving pancreatic head resection (Beger/Frey's procedure)
Distal pancreatectomy with/without splenectomy
Central pancreatectomy
Other

Table III: Predicted morbidity and mortality after surgical resection

Morbidity (Major complications)	Mortality
Pancreatic fistula Anastomotic leak Postoperative bleed Other complications requiring re-laparotomy	30- and 90-day postoperative mortality

Table IV: Potential risk factors of malignancy; patient and cyst related

Patient Characteristics	Cyst Morphology	Cyst Fluid
Age (years)	Number of cysts (Single/Multiple)	Presence Mucin
Sex (M/F)	Cyst size (bidirectional)	Cytology
Body Mass Index (BMI)	Cyst growth	CA 19.9
History of pancreatitis	Location (head, neck, body, or tail)	CEA
History of pancreatic cyst/cancer	Micro- or macrocystic pattern	Amylase
History of pancreatic surgery	Uni- or multilocular	
Family history pancreatic cancer	Internal septa (if yes, enhancing?)	
Family history of breast and/or colon cancer	Cyst wall (thick > 2 mm/thin < 2 mm)	
Symptoms of steatorrhea	Solid components (if yes; enhancing?)	
Diabetes	Calcifications (if yes; central/peripheral)	
Insulin use	Pancreatic duct communication (Y/N)	
Smoking	Main pancreatic duct dilatation (Y/N)	
Alcohol abuse	Common bile duct dilatation (Y/N)	
	Calibre change main PD (Y/N)	
Serum CA 19.9 level		

Table V: Patient Questionnaire

I. History and background (to evaluate risk factors)
 
Height and weight
 
Smoking and drinking habits
 
History of pancreatitis, pancreatic cysts/cancer/surgery, Diabetes, and insulin use
 
Family history of pancreatitis, and breast/colon or pancreatic cancer

II. Worries and burden of investigational procedures
 
Burden of imaging (MRCP/EUS/CT)

III. Questions regarding the general burden of surveillance and cancer worries
 
Regular checking of a pancreatic cyst...
 
 - Is a good way to detect cancer in time. - Lessens my fear to get cancer. - Gives me a sense of security. - Can lead to unnecessary uncertainty. - Is not important to me, since it will be too late to change the outcome of the disease anyway 
To what extent...
 
 - Do you find the check-ups burdensome? - Do the advantages of the check-up outweigh the disadvantages for you? - Are you nervous when you have to come for your check-up visit? - Do you dread the next check-up visit? 
How often would you like to have your pancreatic cyst checked?
 
For how long would you like to be checked?
 
Did the cyst surveillance change the extent to which you worry about cancer?

IV. Hospital Anxiety and Depression Scale
 
I feel tense or wound up.
 
I still enjoy the things I used to enjoy.
 
I get a sort of frightened feeling, as if something bad is about to happen.
 
I can laugh and see the funny side of things.
 
Worrying thoughts go through my mine.
 
I feel cheerful.

I can sit at ease and feel relaxed.

I feel as if I am slowed-down.

I get a sort of frightened feeling, like butterflies in my stomach.

I have lost interest in my appearance.

I feel restless and have to be on the move.

I look forward with enjoyment to things.

I get sudden feelings of panic.

I can enjoy reading a good book or watching a radio or TV programme.

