1. INTRODUCTION AND RATIONALE

Incidental pancreatic cysts are prevalent, in particular in this day and age of cross-sectional imaging[3]. The reported incidence depends on the applied imaging technique and the investigated setting. In CT series of symptomatic patients, the incidence varies from 1 to 3%[4]. In healthy individuals undergoing a screening MRI, we found a pancreatic cyst in 2.4%[5]. An autopsy series by Kimura even reported a prevalence rate of 24%[6].

These cysts form a heterogeneous group of non-neoplastic and neoplastic lesions, with variable pathologic features, clinical presentation, and outcome. Most cysts are (virtually) benign, such as Pseudocysts and Serous Cystadenomas (SCA), and, when asymptomatic, do not require treatment or follow-up. However, some neoplastic cysts have a malignant potential (Mucinous cysts and Intraductal Papillary Mucinous Neoplasms (IPMN)), and require follow-up or even a surgical resection[7, 8]. Unfortunately, to distinguish these pancreatic cysts, especially the smaller ones, is often impossible[9].

A second problem in pancreatic cyst management is that data regarding the natural history and predictive factors for malignant degeneration are virtually lacking.[2, 10]. The literature is biased by highly selected patients series from tertiary referral centres. Sahani reported a 13% risk of malignancy in cysts smaller than 3 cm[2]. In asymptomatic cysts, the reported prevalence of carcinoma varies between 1 and 3%[8]. However, the malignant potential is likely to be much lower, considering the high prevalence of pancreatic cysts and the low incidence of malignant cystic neoplasms. Fitzgerald, for instance, reported a yearly incidence of malignant pancreatic cysts from a state-wide tumour registry in Michigan, USA, of 0.47/100.000[7]. Given the 2.4% incidence of pancreatic cysts on screening MRI's, the calculated malignancy rate would be no more than 0.0002 per year[5].

Because it is impossible to estimate the cancer risk of small pancreatic cysts, treating physicians face a difficult dilemma: to miss a pancreatic carcinoma, or to expose the majority of patients with a benign cystic lesion to redundant investigations, or even unnecessary surgery (with substantial morbidity and mortality). At present, an intensive surveillance strategy is generally chosen, driven out of fear for one of the most deadly cancers.

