5.4 Data collection

Treating physicians will be asked to fill out an online case record form regarding the choice and outcome of the imaging studies, serum and cyst fluid analysis, and the clinical condition of the patient. Patients will fill out questionnaires regarding their quality-of-life and the burden of cyst surveillance.

Any cyst related event will be recorded (i.e. changes in follow-up parameters or strategy, additional imaging studies, reaching an indication for cyst resection, the decision for or against treatment (with motivations), surgical procedures, complications of surgery, pathological outcome). If conservative management is chosen although resection criteria

are met, the argumentation for this decision will be noted. Cyst follow-up will be continued in this group and the subsequent outcome will be monitored. Data collection will continue until August 2024. The database will not only be used for data analysis, but will also automatically generate reminders to the treating physician, regarding follow-up dates.

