6.1.2 Secondary study endpoints

- The outcome of patients with an indication for cyst resection (treated and non-treated), in terms of the number of operated patients, surgical procedures, morbidity, mortality, and cyst recurrence (Table II and III).
- Cyst evolution, in terms of development of symptoms, cyst growth, nodules, and secondary pancreatic duct dilatation.
- The perceived burden of surveillance for participants, as assessed by questionnaires regarding attitude towards surveillance and general anxiety and depression (Hospital Anxiety and Depression scale, HADS) (Table V) [15-19].

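### Table III admits complications other than fistula, leak or bleeding to the operative-morbidity count only through re-laparotomy, so serious events managed otherwise fall outside the tally

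*Protocol*

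**What the plan says.** Section 6.1.2 defines the first secondary endpoint as the outcome of patients with an indication for resection, "in terms of the number of operated patients, surgical procedures, morbidity, mortality, and cyst recurrence (Table II and III"). Table II gives the types of operation and Table III the morbidity and mortality.

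Table III, in the Addendum, is titled "Table III: Predicted morbidity and mortality after surgical resection". Its morbidity column is headed "Morbidity (Major complications") and contains "Pancreatic fistula Anastomotic leak Postoperative bleed Other complications requiring re-laparotomy". Its mortality column reads "30- and 90-day postoperative mortality". Nothing else in the protocol specifies operative morbidity, and no severity grading of complications appears anywhere in it.

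Two other sections bear on the data. Section 5.4 lists, among the cyst-related events to be recorded, "surgical procedures, complications of surgery, pathological outcome", without restricting complications by severity or treatment. Section 7.2 has all adverse events recorded and treats as serious those that are life-threatening or that require or prolong a hospital stay.

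**The concern.** A column headed as major complications should collect the serious ones. This one selects by type for three complications and by one particular treatment for all the rest. A serious event outside the three named types is counted if the surgeon reopens the abdomen and not if it is handled by drainage, endoscopy or intensive care. The count then partly reflects how a hospital manages complications. Section 5.3 leaves management to the treating physician, and section 3 describes an international multicentre cohort, so practice can be expected to vary.

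The component matters to the study's question. The Introduction sets the risk of missing a carcinoma against exposing patients with benign lesions to redundant tests "or even unnecessary surgery (with substantial morbidity and mortality"). Section 8 has the first report describe the endpoints of section 6.1 and then uses those outcome data as input to the MISCAN model. A morbidity figure that omits a class of serious events would understate the harm of resection wherever it is used.

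**Working it through.** The protocol states no figure on this point, so there is nothing to reproduce. The check is to apply Table III to test records under each way it can reasonably be read.

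The readings are:
- **A.** Closed list; fistula, leak and bleed count at any severity.
- **B.** Closed list; the column heading acts as a filter, so only major fistulas, leaks and bleeds count.
- **C.** Closed list; the re-laparotomy condition is meant to qualify all four entries.
- **D.** Illustrative list of expected complications, not a counting rule.

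| Postoperative record (patient survives) | A | B | C | D |
|---|---|---|---|---|
| Pulmonary embolism with intensive care, no re-laparotomy | not counted | not counted | not counted | undetermined |
| Abscess drained through the skin, no fistula | not counted | not counted | not counted | undetermined |
| Serious fistula managed without re-laparotomy | counted | counted | not counted | undetermined |
| Fistula needing no treatment | counted | not counted | not counted | undetermined |

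Four things follow.

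1. The first two records are left out under every closed-list reading. The under-count does not depend on choosing among A, B and C.
2. The last record is counted as major only under A. The wording does not settle whether A is meant, so an over-count is possible but not established.
3. Under C the minor fistula drops out, but serious fistulas, leaks and bleeds managed without re-laparotomy drop out as well, so the under-count grows.
4. Under D the endpoint has no counting rule at all.

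Table II helps to judge whether the list is closed. Its last row is an unrestricted category for other procedures. The corresponding entry in Table III carries a condition, which a purely illustrative list would not need.

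The two columns of Table III also differ on time. Mortality is counted at 30 and 90 days; morbidity has no window.

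On size, let M be the number of truly major complications per 100 resections, q the share of them outside the list, and F the number of minor fistulas counted as major. The tally is M × (1 − q) + F. The documents give none of the three. Purely as an assumed illustration, take M = 25 and q from 20% to 40%. Then 25 × 0.20 = 5 to 25 × 0.40 = 10 events are left out, and 25 − 10 = 15 to 25 − 5 = 20 are counted. Under reading A with an assumed F = 10, the tally becomes 15 + 10 = 25 to 20 + 10 = 30. Under that reading, opposite errors could give a plausible total made up partly of the wrong patients. These figures show the mechanism and are not evidence about this cohort.

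**The case against.** The strongest reply is that Table III was never declared a closed counting rule. Its title speaks of predicted morbidity, section 6.1.2 points to it only in parentheses, and no sentence says that nothing else counts. This stands as far as it goes. But the table is the only specification of operative morbidity in the protocol and the endpoint refers to it. If it is merely illustrative, the endpoint lacks a definition, and the same correction is needed.

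A second reply is that nothing is lost. A reader might infer from Table III that life-threatening complications go unrecorded. The documents do not support that: sections 5.4 and 7.2 capture them, and a broader tally remains possible. The omission concerns the count. Since neither section asks for a severity grade, a later classification would depend on what each centre wrote down.

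A reader might also infer that a trivial fistula is certainly counted as major, so that the rule errs in both directions. That is not established, because the heading or the re-laparotomy phrase may be meant to qualify the named items.

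A third reply is that grading and windows for a descriptive secondary outcome belong in the SAP or the case record form, neither of which is shown. That would hold if the protocol were silent. Here the protocol sets the content of the count itself, and a later document would have to depart from it.

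Finally, importance should not be overstated. This is one component of one secondary endpoint, with no threshold or decision rule attached. The subgroups in section 8.1 are by cyst type, new or previous diagnosis, and imaging modality; no comparison between hospitals or countries is planned. Nor do the documents make operative harm the main cost of surveillance: the Summary and Introduction give at least as much weight to redundant investigations.

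**Conclusion.** The point holds as a defect in how one component of a secondary endpoint is counted. Under any reading that treats Table III as the counting rule, non-fatal serious complications other than fistula, leak or bleed are left out of the morbidity tally unless they led to re-laparotomy. If the table is only illustrative, there is no rule. The status of minor fistulas, leaks and bleeds, and the time window for morbidity, are left open.

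The size of the effect cannot be derived from the documents. Its direction for the omitted class is downward; the net direction of the total is unknown, because it depends on how the three named items are read. The conclusion rests on section 6.1.2 using Table III to specify morbidity and on no other definition being in force. The primary endpoints are unaffected. The change is worth making, but the study's main conclusions do not depend on it.

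**What to change.** Reword the morbidity column of Table III so that major morbidity is any postoperative complication at or above one prespecified standard severity grade within 90 days of resection. Clavien-Dindo III or higher is one workable choice, and 90 days matches the longer mortality window in the same table. List fistula, leak, bleed and re-laparotomy beneath it as types, tabulated separately. State that the tally is derived from the unrestricted complication records of section 5.4.

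This changes measurement only and leaves patient management as it is. It needs new table wording, one grade field on the complication form if the form does not already have one, and retrospective grading of earlier records where the recorded treatment allows. Records too sparse to grade should be reported as such. A grade of this kind still rests partly on the treatment given, so it reduces the dependence on local practice without removing it.
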